#### **8.5.1.6. Calculation of Excretion Parameters (Part 2)**

The amount of the dose administered recovered over each time interval  $t_1$  to  $t_2$  ( $A_{e(t_1-t_2)}$ ) in urine or feces for [ $^{14}\text{C}$ ]-LOXO-305 and total radioactivity will be calculated as the product of urine analyte concentration and urine sample volume or feces analyte concentration and fecal sample weight. Where only urine sample weight is supplied, a specific gravity of 1 g/mL will be assumed, and it will be considered equivalent to urine volume. Cumulative  $A_{eu}$  or  $A_{ef}$  will be calculated by summing the respective matrix  $A_{e(t_1-t_2)}$  values across collection intervals.

The percentage of the dose administered recovered ( $f_e$ ) over each time interval  $t_1$  to  $t_2$  ( $f_{e(t_1-t_2)}$ ) in urine or feces as [ $^{14}\text{C}$ ]-LOXO-305 and total radioactivity will be calculated for each sample collection interval as follows:

$$f_{e(t_1-t_2)} = (A_{e(t_1-t_2)} / \text{dose}) \times 100$$

Cumulative  $f_{eu}$  or  $f_{ef}$  will be calculated by summing the respective matrix  $f_{e(t_1-t_2)}$  and combined matrix  $f_{e(t_1-t_2)}$  (urine + feces) values in the same manner as  $A_{eu}$  and  $A_{ef}$ .

Renal clearance ( $CL_R$ ) will be calculated over 0- $t_2$  according to the following formula, where cumulative  $A_{eu}$  and plasma AUC are calculable to the same end time ( $t_2$ ):

$$CL_R = A_{eu0-t_2} / AUC_{0-t_2}$$

Alternatively,  $AUC_{0-\infty}$  may be used if urinary excretion of the dose is considered to be complete and  $AUC_{0-\infty}$  is well characterized.

#### **8.5.1.7. Criteria for Handling Below the Limit of Quantification or Missing Concentrations for Pharmacokinetic Analysis**

Plasma and whole blood concentrations BLQ will be assigned a value of 0 before the first measurable concentration and thereafter BLQs will be treated as missing. The following rules apply with special situations defined below:

- If an entire concentration-time profile is BLQ, it will be excluded from PK analysis.
- Where 2 or more consecutive concentrations are BLQ at the end of a profile, the profile will be deemed to have terminated and any further quantifiable concentrations will be set to missing for the calculation of the PK parameters, unless they are considered to be a true characteristic of the profile of the drug.
- If a predose plasma or whole blood concentration is missing, it will be set to zero by default within Phoenix WinNonlin.

Urine or feces concentrations that are BLQ will be set to zero for the calculation of  $A_{eu(t_1-t_2)}$  and  $A_{ef(t_1-t_2)}$ , respectively.

### **8.5.1.8. Treatment of Outliers in Pharmacokinetic Analysis**

If a value is considered to be anomalous due to being inconsistent with the expected PK profile, it may be appropriate to exclude the value from the PK analysis. However, the exclusion of any data must have strong justification and will be documented in the CSR.

Any quantifiable predose concentration value will be considered anomalous and set to missing for the PK analysis.

### **8.5.2. Presentation of Pharmacokinetic Data**

Individual concentrations deemed to be anomalous will be flagged in the listings and excluded from the summary statistics.

For PK concentration data the following rules will apply:

- Values that are BLQ will be set to 0 for the calculation of summary statistics.
- Arithmetic mean or median values that are BLQ will be presented as 0.
- If any BLQ results (treated as 0) are in a series of summarized data, geometric mean and CV% of geometric mean will be reported as not calculated (NC).
- If there are fewer 1 than 3 values in the data series, only the minimum, maximum and N will be presented. The other summary statistics will be denoted as not calculated (NC).

For PK parameters the following rule will apply:

- Geometric mean and coefficient of variation will not be calculated for  $t_{last}$  or  $t_{max}$ .

PK analysis will use actual times as recorded on the electronic case report form.

### **8.5.3. Pharmacokinetic Statistical Methodology**

All PK concentrations and parameters will be listed.

Summary tables by part, mean (+ standard deviation [SD]) figures, overlaying individual figures, and individual figures by time postdose will be provided for plasma and whole blood PK concentrations. All figures will be produced on both linear and semi-logarithmic scales. The +SD bars will only be displayed on the linear scale.

Summary tables by part will be provided for all PK parameters, with the exception of diagnostic regression-related PK parameters. Summary statistics (n, Mean, SD, CV%, minimum, median, maximum, geometric mean [Geom Mean] and geometric CV% [Geom CV%]) will be calculated for plasma LOXO-305 PK parameters. Excluded subjects will be listed in the PK parameter tables, but will be excluded from the summary statistics and noted as such in the tables.

Separate summary tables by time interval will be provided for excretion parameters and cumulative excretion parameters.

No inferential statistical analyses are planned.

## 8.6. Safety and Tolerability Assessments

### 8.6.1. Adverse Events

All AEs will be coded using the Medical Dictionary for Regulatory Activities (MedDRA) Version 23.0. All AEs will be assigned severity grade using National Cancer Institute Common Terminology Criteria for Adverse Events (CTCAE) Version 5.0.

A treatment-emergent adverse event (TEAE) will be defined as an AE that starts during or after the first dose, or starts prior to the first dose and increases in severity after the first dose.

A treatment-related TEAE will be defined as a TEAE with a relationship of related to the study treatment, as determined by the investigator.

All AEs will be listed. In addition to the data recorded in the database, the listings will include derived onset time and duration. Onset time will be calculated from the time of dosing for TEAEs only.

The frequency of subjects with TEAEs and the number of TEAEs will be summarized by part for the following categories:

- TEAEs (overall, serious, leading to discontinuation, and leading to death) by part
- TEAEs by severity and part
- Treatment-related TEAEs (overall, serious, leading to discontinuation, and leading to death) by part
- Treatment-related TEAEs by severity and part

The frequency of subjects will be summarized separately for TEAEs and treatment-related TEAEs by the following:

- System organ class and preferred term
- Preferred term and treatment/part
- System organ class, preferred term, day of onset, and treatment/part

For the AE data the following rules will apply:

- For the derivation of TEAE status: If the start date/time of an AE is incomplete or missing, an AE will be assumed to be a TEAE, unless the incomplete start date/time or the end date/time indicates an AE started prior to dosing.
- For the derivation of treatment-related TEAE status: If the study treatment relationship for a TEAE is missing, a TEAE will be assumed to be a treatment-related TEAE.

- For the derivation of onset time: If the start date/time of an AE is missing, onset time will not be calculated. If the start date/time of an AE is incomplete, where possible, the minimum possible onset time will be calculated and presented in ‘ $\geq$ DD:HH:MM’ format (eg, if the date/time of dosing is 01MAY2019/08:00 and recorded start date/time of an AE is 03MAY2019, then the minimum possible onset time will be calculated by assuming the AE started at the first hour and minute of 03MAY2019 [03MAY2019/00:00], thus will be presented as onset time  $\geq$ 01:16:00 in the listing).
- For the derivation of duration: If the end date/time of an AE is missing, duration will not be calculated. If the start or end date/time of an AE is incomplete, where possible, the maximum possible duration will be calculated and presented in ‘ $\leq$ DD:HH:MM’ format (eg, if the start of an AE date/time is 01MAY2019/08:00 and its recorded end date/time is 03MAY2019, then the maximum possible duration will be calculated by assuming the AE ended at the last hour and minute of 03MAY2019 [03MAY2019/23:59], thus will be presented as duration  $\leq$ 02:15:59 in the listing).
- For the calculation of summary statistics: If the severity of a TEAE is missing, a TEAE will be counted under the maximum severity possible, up to Grade 4 in the absence of a fatal outcome.
- For the calculation of summary statistics: If a subject experienced multiple TEAEs with the same preferred term for the same treatment, this will be counted as 1 TEAE for that treatment under the maximum severity recorded.

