## 5. SAMPLE SIZE JUSTIFICATION

No formal statistical assessment of sample size has been conducted as this study does not have a hypothesis. The sample size chosen for this study is common in human radiolabeled studies and is considered sufficient to achieve the objectives of the study. Six subjects will participate in each part of the study. Each subject will participate in either Part 1 or Part 2, but not both. In the event of early withdrawal of any subjects and/or to ensure 6 subjects complete each part of the study, replacement subjects may be enrolled at the discretion of the Sponsor.

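### SAP 8.6.1 promises the number of TEAEs, but its unrestricted counting rule, applied as written, understates that number whenever a subject has repeat events of the same preferred term

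*SAP*

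**What the plan says.** All the relevant text is in SAP section 8.6.1.

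- The first group of tables carries both subject and event counts: "The frequency of subjects with TEAEs and the number of TEAEs will be summarized by part for the following categories". The categories are TEAEs overall, serious, leading to discontinuation and leading to death; "TEAEs by severity and part"; and the same two sets for treatment-related TEAEs, including "Treatment-related TEAEs by severity and part".
- The second group, by system organ class, preferred term and day of onset, carries subject counts only: "The frequency of subjects will be summarized separately for TEAEs and treatment-related TEAEs by the following".
- The counting rule is the last of the AE data rules. Its condition is "For the calculation of summary statistics: If a subject experienced multiple TEAEs with the same preferred term for the same treatment", and its consequence is "this will be counted as 1 TEAE for that treatment under the maximum severity recorded".
- Individual events are kept outside the tables: "All AEs will be listed".

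SAP section 6 gives one treatment name per part, so the same-treatment condition is always met within a subject. Protocol section 8.4 asks for AE incidence by severity and relationship and for TEAEs by system organ class and preferred term. It contains no rule that collapses repeats.

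**The concern.** Counting a subject once per preferred term at the worst grade is the usual convention for subject incidence. Here it is worded in units of events, and its scope is summary statistics without limit. The tables that report a number of TEAEs fall within that scope, and no other rule in the SAP says how events are to be counted.

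A programmer who follows the text would therefore put subject-by-term pairs under a label that says number of TEAEs. Another could reasonably count every record. Protocol section 8.5 has the tables programmed from the final SAP and peer reviewed by an independent programmer, so the text needs to yield one answer.

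Safety and tolerability is the secondary objective of both parts. What is at stake is the event column of the overall and by-severity tables, and its agreement with the listing.

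**Working it through.** The plan has no figure of its own to reproduce on this point, so the check applies the rule literally and compares the result with a count of recorded events.

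**Inputs from the SAP.** Event counts are promised for the overall and severity categories (8.6.1). The rule covers summary statistics generally (8.6.1). On numbers: "Six subjects will participate in each part of the study" (section 5).

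**Formulae.** Let n(i,j) be the number of TEAEs with preferred term j in subject i.

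- Events recorded = sum of n(i,j).
- Count under the rule = number of pairs (i,j) with n(i,j) ≥ 1.
- Shortfall = sum of (n(i,j) − 1) over those pairs. It is zero when nobody has a repeat.
- Severity under the rule: each pair adds one to its highest grade and nothing to any other grade.

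**Worked example (assumed data, one part of six subjects).** Subject A has headache at Grades 1, 1 and 2. Subject B has nausea at Grades 1 and 1. Subject C has dizziness at Grade 1. The other three have no TEAE.

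| | Every event counted | Rule as written |
|---|---|---|
| Number of TEAEs | 3 + 2 + 1 = 6 | 1 + 1 + 1 = 3 |
| Grade 1 | 2 + 2 + 1 = 5 | 2 |
| Grade 2 | 1 | 1 |
| Subjects with a TEAE | 3 | 3 |

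The shortfall is (3 − 1) + (2 − 1) + (1 − 1) = 3 events, all Grade 1. The subject row does not change.

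**Range over an assumed repeat rate.** Suppose the events of one term in one subject are Poisson with mean m. The expected number of events is m and the expected count under the rule is 1 − exp(−m), so the relative shortfall is 1 − (1 − exp(−m))/m. For m = 0.5 this is 1 − 0.3935/0.5 = 21.3%.

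| m (assumed) | Shortfall |
|---|---|
| 0.05 | 2.5% |
| 0.1 | 4.8% |
| 0.25 | 11.5% |
| 0.5 | 21.3% |
| 1 | 36.8% |
| 2 | 56.8% |

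These values show how the shortfall grows with the repeat rate. They do not predict its size in this trial.

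**The case against.** The best defence is a narrower reading. The rule is keyed to preferred term, and the tables broken down by preferred term report subjects only, where the rule does no harm. The tables that promise event counts are not organised by term, so an analyst might apply the rule to subject incidence alone. The text does not say so, and two features count against it. The rule's unit is one TEAE, not one subject. Its reference to maximum severity matters mainly in the severity tables, where event counts are promised.

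A second defence is that the TFL shells, which SAP section 1 says describe the planned tables in detail, may show that the event column counts every record. They are not among the documents reviewed, so this is possible. It would leave the SAP sentence in need of the same correction.

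Other points limit the concern and stand in full. Each part gives single doses to six healthy men, so repeats may be few or absent. The protocol's request for incidence is met either way.

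A reader might infer more than the documents support:

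- That the counts are certain to be too low. They are too low only if a subject has repeats of the same term.
- That lower-grade events disappear from the report. They drop out of the summary counts and remain in the listing.
- That repeats are moved up to the worst grade. They are dropped: Grades 1, 1 and 2 become one Grade 2 event, not three.
- That a particular percentage undercount can be expected. No repeat rate is given from which to derive one.

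**Conclusion.** The point holds in conditional form. As written, the rule turns the promised number of TEAEs into a count of subject-by-preferred-term pairs. Whenever a subject has repeat events of one term, the overall and by-severity event counts are too low, and repeats of the same or lower grade are missing from them. The totals then disagree with the AE listing.

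The size cannot be fixed from the documents and may be zero. With six subjects per part, a few repeats are enough to change a total visibly. The conclusion assumes that the SAP sentence is followed literally and that the shells do not override it. The matter is minor: it affects a supplementary count in a descriptive safety summary, and no subject frequency, listing or PK result changes.

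**What to change.** Reword the last AE data rule in SAP 8.6.1 in two parts. First, for frequency-of-subjects summaries, each subject is counted once per preferred term, at the maximum severity recorded. Second, the number of TEAEs counts every recorded TEAE, each under its own severity. Check that the event columns in the TFL shells follow the same definition.

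The cost is one SAP sentence before database lock, with no new data and no change to the design. If event counts are not wanted, the alternative is to drop the promise of them from the section.

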### **8.6.2. Clinical Laboratory Parameters**

All clinical laboratory parameters, with changes from baseline, will be listed; any value outside the clinical reference range will be flagged, and whether the out of range value was deemed clinically significant or not clinically significant will be indicated. Separate listings will be provided for any parameter for which there is any individual subject value outside the respective clinical reference range.

The observed results and change from baseline for clinical chemistry, hematology, and coagulation parameters will be summarized descriptively by study part and timepoint.

Values recorded as  $< x$ ,  $\leq x$ ,  $> x$ , or  $\geq x$  will be displayed in the listings as recorded. For the derivation of listing flags, calculation of summary statistics, and presentation in the figures,  $< x$  and  $\leq x$  values will be set to 0 whereas  $> x$  and  $\geq x$  values will be set to  $x$ .

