Alanine aminotransferase (ALT)	Hematocrit	Coagulation Parameters:
Albumin Alkaline phosphatase (ALP) Amylase Aspartate aminotransferase (AST) Bilirubin (direct and total) Blood urea nitrogen Calcium Chloride Cholesterol Creatine kinase Creatinine Glucose Iron	Hemoglobin Mean corpuscular hemoglobin Mean corpuscular hemoglobin concentration Mean corpuscular volume Platelet count Red blood cell (RBC) count RBC distribution width White blood cell (WBC) count WBC differential (percent and absolute): Basophils Eosinophils Lymphocytes	Partial thromboplastin time Prothrombin time International normalized ratio Serology: ^b Human immunodeficiency virus (HIV) antibody Hepatitis B surface antigen (HBsAg) Hepatitis B virus (HBV) core antibody Hepatitis C virus (HCV) antibody
Lipase	Monocytes	antioody
Magnesium	Neutrophils	
Phosphorus Potassium	Urinalysis:	Other Tests:
Sodium Total protein Triglycerides Uric acid	Bilirubin Color and appearance Glucose Ketones	Hemoglobin A1c (HbA1c) ^b Estimated glomerular filtration rate ^{a,c} Thyroid-stimulating hormone
Urine Drug Screen: ^a	Leukocyte esterase Nitrite	(TSH) ^b SARS-CoV-2 (COVID-19) test
Including but not limited to the following: Alcohol (ethanol) Amphetamines Barbiturates Benzodiazepines Cannabinoids Cocaine (metabolite) Methadone Opiates Phencyclidine Cotinine	Occult blood pH and specific gravity Protein Urobilinogen Microscopic examination including bacteria, casts, crystals, epithelial cells, RBCs, and WBCs (if protein, leukocyte esterase, nitrite, or blood is positive)	5AK5-C0 v -2 (CO v ID-13) test

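### SAP 8.6.2 sets laboratory results reported with an inequality to 0 or to the reporting limit before flagging and summarising, which can misplace out-of-range flags and put an impossible 0 in the INR summary

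*SAP*

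**What the plan says.** SAP 8.6.2 (Clinical Laboratory Parameters) has four elements that bear on this.

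- **Display.** Results recorded with an inequality sign "will be displayed in the listings as recorded".
- **Substitution.** For other purposes, `<x` and `<=x` "values will be set to 0 whereas" `>x` and `>=x` become x. The scope is given as: "For the derivation of listing flags, calculation of summary statistics, and presentation in the figures". No test or panel is exempted.
- **Flagging.** In the listings, "any value outside the clinical reference range will be flagged". Each such value also carries an indicator of clinical significance. Out-of-range values have a further consequence: "Separate listings will be provided for any parameter for which there is any individual subject value outside the respective clinical reference range".
- **Summaries.** Observed values and changes from baseline are summarised for chemistry, hematology and coagulation. Urinalysis is not in that list.

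The panel in Protocol Appendix 2 includes "International normalized ratio" under coagulation and "pH and specific gravity" under urinalysis. SAP 8.1.3 defines change as the value at the timepoint minus the baseline value.

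**The concern.** A result known only to lie below x is treated as the lowest value there is. A result known to lie above x is treated as lying exactly at x. Comparing either substitute with a reference limit can give an answer that the recorded result does not support.

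The flag also does more than mark a line. Being out of range is what brings a parameter into the separate listing and what the clinical-significance indicator is attached to. A missed flag can therefore take a high result out of the output designed to show it. In the summaries, 0 is a possible value for some tests but not for INR, so a table could show a minimum that no subject can have. With six subjects per part, one such value visibly moves the mean and the SD.

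**Working it through.** The plan states no figure to reproduce, and neither document gives reporting limits or reference ranges. The check applies the rule to a general limit x. I take out of range to mean strictly below the lower limit (LLN) or strictly above the upper limit (ULN).

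**1. Flags**

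| Recorded | Position of limit | Value used | Flag under the rule | What the record supports |
|---|---|---|---|---|
| `<x` | LLN = 0 | 0 | none | none: correct |
| `<x` | 0 < LLN < x | 0 | low | low or normal: unsupported low |
| `<x` | LLN at or above x | 0 | low | low: correct |
| `<=x` | 0 < LLN < x | 0 | low | low or normal: unsupported low |
| `<=x` | LLN = x | 0 | low | low, or exactly at the limit and normal: unsupported low |
| `>x` | ULN < x | x | high | high: correct |
| `>x` | ULN = x | x | none | high: certain miss |
| `>x` | ULN > x | x | none | undetermined |

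Take urine specific gravity as an illustration, with an assumed range of 1.005 to 1.030. A result of `<=1.005` becomes 0 and is flagged low, although 1.005 itself is normal. A result of `>1.030` becomes 1.030 and is not flagged, although every value it can stand for is high.

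**2. INR summary**

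Assume that one of six subjects goes from 1.0 to `<0.9` and that the other five do not change.

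- Under the rule, the subject's change is 0 - 1.0 = -1.0. The mean change is -1.0/6 = -0.167, with SD 0.41, and the minimum INR shown is 0.
- With x substituted, the change is 0.9 - 1.0 = -0.1. The mean change is -0.1/6 = -0.017, with SD 0.04.

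**3. General bound for summaries**

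One `<x` result among six lowers the mean by x/6 = 0.167x relative to using x, and by (x/2)/6 = 0.083x relative to using x/2. Assume the other five values are 1.1x, with sum 5.5x:

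| Substitute | Mean | SD |
|---|---|---|
| 0 (SAP rule) | 5.5x/6 = 0.917x | 0.449x |
| x/2 | 6.0x/6 = 1.000x | 0.245x |
| x | 6.5x/6 = 1.083x | 0.041x |

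**4. Change from baseline**

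Take a baseline b of at least x and a later `<x`. The rule gives -b, while the true change lies between -b and -(b - x). The fall is overstated by at most x.

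- For b = 1.1x, the rule gives -100%, against -0.1x/1.1x = -9.1% with x and -0.6x/1.1x = -54.5% with x/2.
- For b = 10x, it gives -100%, against -90% and -95%.

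A baseline of `<x` followed by a measured value overstates the rise, again by at most x. If both values are `<x`, the change is 0. A later `>x` after a lower measured baseline gives x - b, which understates the rise.

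**The case against.** The case for leaving the rule alone is substantial.

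- **Everything is conditional.** Where the lower limit is 0, or x lies beyond the range limit, the flags are right. Nothing shows that this laboratory reports INR or specific gravity with an inequality, so the frequency could be zero. This stands, and it is why the point says only what the rule can do.
- **The recorded result stays visible.** A reader might infer that the original results are overwritten throughout. They are not, because the listings keep the inequality sign. That lets a reader discount a false low, but it does not restore a missing flag or a missing entry in the separate listing.
- **Urinalysis is not summarised.** A reader might infer that a specific gravity set to 0 would distort a group mean or a tabulated change. The SAP does not support that. It also does not say whether individual changes in the listings use substituted values.
- **Changes are not inflated in general.** Overstatement is confined to the `<x` side and bounded by x. The `>x` side works the other way.
- **For concentration-type tests, x is no better than 0.** Both have a worst-case error of x, in opposite directions; x/2 halves it. Where 0 is a possible value, the choice is largely convention.
- **Safety review does not rest on the programmed flag.** Abnormalities noted in laboratory evaluations are recorded as adverse events on the investigator's judgement (Protocol 7.2.1 and Appendix 1). Results are also to be available to the investigator before release from the unit (Protocol Appendix 4). A missed flag is a reporting fault and does not remove that review.

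**Conclusion.** The point holds in limited form. Three wrong outputs follow from the rule as written: an unsupported low flag, a certain high left unflagged and so not brought into the separate out-of-range listing, and a 0 in the INR summary. Each depends on where the reporting limit sits relative to the reference range, so neither frequency nor actual size can be established from the documents. The INR and specific gravity figures above are assumed examples.

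The severity is minor. These are secondary, descriptive safety data with six subjects per part and no inferential analysis (SAP 8.6.6). The documents do not support the stronger conclusion that the laboratory summaries are generally distorted.

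**What to change.** Replace the substitution sentence in SAP 8.6.2 with two rules.

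1. **Flags from the recorded inequality.** `<x` is low if x is at or below the lower limit; `<=x` is low only if x is below it. `>x` is high if x is at or above the upper limit; `>=x` is high only if x is above it. Otherwise there is no automatic flag.
2. **Summaries and figures.** Do not substitute 0 for tests that cannot be 0, such as INR; use x there. The substitution for concentration-type tests (0, x/2 or x) is a convention and need not change.

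It would help to add a clause saying whether listed individual changes from baseline use substituted values.

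The cost is a few lines of SAP text and a small programming change before database lock. No assessment, sample or subject is affected.
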